## ■ Objective

The main goal of this study is to test the efficacy of a peer-facilitated telemedicine HCV treatment implementation strategy for people who use drugs versus local HCV treatment referral for achieving HCV sustained viral response at 12 weeks post-treatment (SVR12).

## Background

Untreated drug use is associated with increased hepatitis C (HCV) risk. People living in rural areas – with limited access to prevention and treatment resources – may be particularly susceptible to unchecked HCV transmission. A recent analysis identified six rural county characteristics associated with acute HCV infection rates - mainly due to injection drug use - including drug-overdose deaths, prescription opioid sales, per capita income, white non-Hispanic race/ethnicity, unemployment, and limited buprenorphine prescribing capacity.

HCV transmission is primarily driven by injection drug use. As a result, HCV is endemic among people who used drugs (PWUD). Guidelines state that HCV treatment should be prioritized among patients with substance use disorders, yet only a small percentage (<10%) of PWUD access treatment. The advent of newer highly effective, direct-acting anti-HCV treatments provides an opportunity to limit or even eradicate HCV. However, realizing treatment benefits depends on whether PWUD can be identified, tested, and linked to care, and many PWUD in rural communities struggle to engage with traditional health settings and testing mechanisms. In particular, venipuncture based diagnostics can be traumatizing and challenging for people with current or past injection drug use. Several studies held outside of the United States have suggested improved test acceptance with dried blood spot (DBS) versus traditional venipuncture by as much as four fold and test operating characteristics where acceptable. These tests have not yet been validated for use in the United States with commercial laboratories. For this purpose, we will implement the study in two phases. Phase 1; validating the DBS testing measures, Phase 2; implementing telemedicine hepatitis C treatment after DBS diagnosis. Continuing to phase 2 will not be contingent on phase 1.

New systems of care delivery that integrate HCV treatment in rural areas are urgently needed. Telehealth interventions, which directly connect patients to remote treatment providers, are a potential solution which may support HCV treatment uptake in rural areas. Peer support specialists are people with lived experience in recovery who reach, engage, and retain hard-to-reach populations. They utilize their past shared experiences drug use and recovery to develop rapport and link patients to care. Peer support specialists can facilitate HCV testing and linkage to telehealth HCV treatment for people who use drugs.

**Study Design** Non-blinded, randomized controlled trial. In-depth qualitative interviews assess attitudes and barriers to treatment.

The study will be implemented in two phases; Phase 2 is not contingent on Phase 1.

## **Study Population**

### **a) Number of Subjects**

In Phase 1, potential participants will be pulled from a convenience sample at a Portland clinic providing care for the urban area. An initial target sample of 100 Hepatitis C positive participants will be enrolled for DBS validation. Power will be reassessed based on feedback from receiver operating curve model and additional participants enrolled up to a total of 100 Hepatitis C Positive participants, if necessary. A total of 500 potential participants can be screened expecting 1 in every 4 participants will be positive HCV.

In Phase 2, rural peer care coordinators (PCCs) and research assistants recruit up to 200 PWUD participants from high-needs rural Oregon counties. Study staff specifically target untreated populations recruited from local syringe exchange programs and direct community outreach (e.g. community barbeques, parks, homeless shelters, food pantries, etc.). Participants are encouraged to refer others for study screening.

A subset of up to 40 study participants will complete in-depth qualitative interviews regarding their experiences of hepatitis C treatment.

## **Inclusion and Exclusion Criteria**

### Phase 1: Initial DBS Validation Aim

Participants are eligible for inclusion if they:

- 1) present in person to Central City Concern (CCC) health services for other critical needs
- 2) elect to screen for hepatitis C, HIV, and hepatitis B while waiting for other health service completion
- 3) are age 18 years or greater

Participants are excluded if they:

- 1) inability to perform consent, DBS testing, or incentive distribution without increasing participant social exposure or personal protective equipment utilization
- actively receiving HCV treatment

### Phase 2: TeleHepC Aim

Participants are eligible for inclusion if they:

- 1) live in the study area
- 2) have injected drugs or report recreational opioid use without injection in the last 90 days
- 3) are age 18 or greater
- 4) have chronic active, untreated hepatitis C (defined as positive HCV RNA)
- 5) are seeking treatment for hepatitis C infection.
- 6) are able to communicate in English (this is due to the fact that less than 5% of the population in which we are targeting will be non-English speaking; see "Non-English Speaking Subjects" for additional information).
- 7) are enrolled in health insurance

Participants are excluded if they:

- 1) Have decompensated cirrhosis, defined as Child-Turcotte-Pugh (CTP) score of 7 or greater, or CTP B cirrhosis. CTP scoring is a composite of laboratory metrics (bilirubin, albumin, PT/INR) and clinical findings, including:
  - a. increased abdominal or lower extremity swelling
  - b. confusion consistent with hepatic encephalopathy
- 2) Are pregnant or breastfeeding

**b) Vulnerable Populations**

**Children:** Children will not be included in the study; subjects age 18 and greater are eligible for inclusion.

**Prisoners:** This study is likely to enroll persons involved in the criminal justice system related to substance use. The study will not recruit persons incarcerated/detained in a correctional facility or currently considered “prisoners” by local or state laws, but will not exclude parolees or probationers. Those participants who become incarcerated during the course of their involvement with this study will continue to be followed to ensure safety and data integrity. If necessary, specific documents for incarcerated participants will be developed and approved by the OHSU IRB. Appropriate progress notes will be written to ensure complete documentation of any interaction with an incarcerated participant, specifically mentioning confidentiality procedures.

The project has been granted a federal Certificate of Confidentiality. An OHRP Prisoner Research Certification Letter will be filed through the OHSU IRB and distributed to the sites. Local sites will be covered by both OHSU’s Certificate of Confidentiality and the OHRP Prisoner Certification to enable study follow up visits for participant who may become incarcerated.

**c) Non-English Speaking Subjects**

Oregon opioid use disorder demographics suggest the Oregon Hispanic/Latino population has been relatively spared from this epidemic. Hispanic/Latino patients accounted for 3.7% of opioid use disorder treatment admissions in the North Coast and Southwest Oregon grant target regions in 2015, and nearly all speak English. We consequently anticipate a very small fraction of study participants will be monolingual Spanish speaking. The very small numbers provide insufficient statistical power to assess differences by language group. We thus believe that collecting Spanish language data is not justified on scientific grounds for this study.

**Setting**

**Participating Sites:**

1 Oregon Health & Science University (OHSU) leads the project, under the direction of [name]. OHSU will participate in data quality assurance during study implementation analysis, train PCCs and research assistants (RAs) in study procedures, conduct analyses, and disseminate qualitative and quantitative results. HIV Alliance and Comagine are deferring to OHSU’s IRB; the Oregon Health Authority will be using its own IRB for project review.

2 HIV Alliance is a community based service organization providing support for HIV and HCV treatment and prevention and syringe exchange services in rural Oregon counties. HIV Alliance outreach workers will serve as intervention PCCs. HIV Alliance PCCs will recruit and provide linkage to care for PWUD, and an HIV Alliance research assistant staff will support HIV Alliance syringe exchange staff in collecting survey and laboratory data.

3. Bay Area First Step (BAFS) is a community based service organization that provides housing, and peer-delivered services designed to support individuals and families. BAFS peer mentors will serve as intervention PSSs. BAFS PSSs will recruit and provide linkage to care for PWUD and collect survey data. BAFS plays an active role in the community and has strong relationships with potential participants.

4. Comagine conducts qualitative focus groups and interviews and lead the qualitative analysis.

5. Oregon Health Authority investigators will assist in administrative support of tele-HCV treatment and advise the study team on implementation, interpretation, and dissemination of study findings.

6. Implementation Locations: The study catchment area includes Douglas, rural Lane, Josephine, Coos, Curry, Tillamook, Umatilla, and Clatsop counties.

7. Central City Concern: CCC is a community-based homelessness services organization located in Portland, Oregon. They will participate as the Phase 1 site for DBS validation. CCC hepatitis C team staff will perform usual HCV screening and linkage-to-care interventions, consent individuals for DBS validation study inclusion, perform DBS testing, and deliver and track incentives.

8. Oregon Washington Health Network (OWHN) is a community-based network that addresses mental and physical health, and houses peer support specialists. Peer support specialists will recruit participants and facilitate telemedicine appointments. The OWHN research assistant will consent participants and conduct study assessments.

#### **d) Recruitment Methods**

##### **Participant Recruitment:**

Phase 1: Central City Concern continues to screen for and treat hepatitis C during the COVID-19 pandemic providing clients are presenting in-person for other critical health services. Individuals are offered HCV screening by clinic intake and HCV team staff. CCC clients on campus who opt-in to screen for hepatitis C will be offered venipuncture screening and confirmation labs as per usual clinical practice. After assent to testing, individuals will offer optional participation in DBS validation study.

Participants will receive \$30 upon completion of DBS test.

Phase 2: HIV Alliance already supports syringe exchange and rapid HIV/HCV screening in Douglas, Lane, Josephine and Coos Counties. Community-based syringe exchange programs will serve as initial recruitment sites and supplemented with community settings (e.g. parks, homeless shelters, community barbeques, etc.). Research staff will also approach participants of the Oregon HOPE study who have previously consented to be contacted for future research and offer them study participation. Our preliminary data suggest that HCV treatment is highly sought-after by PWUD in intervention counties.

This project will use **snowball** sampling to recruit participants. Research staff will encourage participants to use their personal networks to invite individuals who may be interested in partaking in the intervention. There will not be incentives provided for referrals or a specific set number of participants encouraged to recruit.

**Compensation:** Participants will receive compensation in the form of cash if they are located in Douglas, Josephine, Coos, Curry or Josephine County. OWHN participants will receive compensation in the form of Visa gift cards.

In the event a participant becomes incarcerated, with their permission, the study team may give their study compensation to a friend or family member to pass along to them so they may have access to it while incarcerated. If the participant does not give permission, compensation will be given to participant when they are able to receive it.

Activity	Cash or gift card Incentive Amount
Prescreen/ Rapid Test/ Blood Draw/ Dried Blood Spot Testing, Full Consent	\$20
Screening blood draw	\$20
*If necessary* second blood draw for missed blood draws	\$20
Return for Results and Baseline Survey	\$15
4 - Week survey	\$20
End of treatment survey	\$30
*12-weeks after end of treatment survey	\$20
*12-weeks after end of treatment blood draw	\$40
36 weeks after end of treatment survey, reinfection labs	\$30
Total	\$215

#### **Cash Incentives:**

Tracking systems will be handling cash compensation. The RA will document the serial number of each bill upon obtaining the cash and again when distributing cash to the participant. Research staff will internally audit and count cash incentive records each week. The Quality Assurance staff member will audit monthly. When carrying cash in the field, only small, pre-counted amounts of cash will be carried. These will be kept in a locked box in a discrete location of the vehicle.

Study participants may choose to seek substance use treatment at residential treatment facilities. Some residential facilities discourage or prohibit patients from having cash at the facility while in treatment. When a study participant is a patient of such a facility and continues to engage in study visits and activities, field staff will hold their study incentives in a locked box at the study office, and distribute funds to the participant when they leave residential treatment.

#### **Gift Card Incentives:**

Tracking systems will be handling electronic gift cards. The RA will document the gift card number upon distribution. Research staff will internally audit the gift card count. The electronic gift card tracking sheet will be kept in a secure folder on Box

#### **e) Consent Process**

##### Phase 1:

Potential participants will be consented by IRB-approved CCC HCV team staff at the time of usual care.  
Extreme efforts will be made to ensure potential participants are able to maintain social distancing  
precautions before, during, and after the engagement with the HCV team. Consent will be offered at the time of testing in a private room one on one with HCV team staff using existing COVID-19 protocol screening practices, consisting of N95 mask and face shield for staff and surgical mask for participants. All surfaces, pens used for consent, and high touch surfaces will be sterilized as per CCC practices. Staff will remind consenting participants that participation is voluntary and that they may withdraw their consent at any time. Participants will be assessed for understanding of study procedures.

##### Phase 2:

People who use drugs will be consented by IRB-approved research assistants, Peer Care Coordinators or syringe exchange outreach staff employed by HIV Alliance who have completed human subjects training. The consent process will take place in a private area with only the participant and the Peer Care Coordinator or syringe exchange outreach staff present. In cases where PWUD are consented in

community-based settings (e.g. parks, etc.), research staff and peers will make sure they are out of hearing distance of others for consent and data collection. Peer care coordinators or syringe exchange outreach staff will remind consenting participants that participation is voluntary and that they may withdraw their consent at any time. Participants will be assessed for understanding of study procedures.

## ■ Procedures

### **Phase 1 Procedures:**

#### **Prescreening Procedures:**

Participants presenting for standard of care HCV, HIV, and HBV screening will consent to Phase 1 of the study using a full consent form. This includes consent for:

- Blood draw for hepatitis C RNA and hepatitis B core Antibody
- Dried Blood Spot card testing procedure (RA or self-administered)
- Blood samples to be shipped to an external lab

All labs will be reviewed by the study clinicians except for the DBS card and serum lab specimens collected for DBS validation, which will not be used for clinical decision making. The serum lab specimens collected for DBS validation will only be sent to Molecular Testing Laboratories for the purpose of DBS card validation and results will not be relayed to the participant.

Chart abstraction will be performed in order to collect basic demographic information. Past lab test results will also be abstracted in order for comparisons to be performed.

### **Phase 2 Procedures:**

#### **Pre-Screening Procedures:**

The HCV rapid test will be optional. If participants self report a positive HCV test previously, they can enroll in the study by self-disclosure of +HCV. If their HCV status is unknown, a rapid test will be performed. If a positive rapid test in the past is reported, an optional rapid test can be completed as part of the study. People who test negative have the option to retest at 6 months. It is anticipated that a significant number of potential participants will screen negative for HCV. If a participant opts to have the HCV rapid test done, a positive result is an eligibility requirement for the study. Participants will be asked to sign a full consent form to indicate consent for rapid HCV testing, Inclusion/Exclusion checklist, and Locator Form completion—as well as the screening phase, randomization, and treatment arm interventions. Upon consent, establishment of baseline known positivity and treatment experience, peers or RAs will perform point of care HCV rapid antibody testing ([OraQuick® HCV Rapid Antibody Test](#)). (See figure 1: Telemedicine Study Flow Diagram). The HCV Rapid Antibody Test is a finger prick that can either be administered by study staff or self-administered, depending on participant and/or staff preference. If it is decided that a self-administered test will be performed, participant will be given an instruction sheet on how to administer the test. Study staff will be present to answer questions and ensure the procedures are correctly followed. Study staff will assist participant in registering for Medicaid Accountable Care Organization (ACO), if needed and applicable.

Upon positive rapid HepC test, participants will be moved to the screening phase. Those with a negative rapid HepC test are not eligible for the study.

Peers and/or RAs will assist participants with reactive tests to go to a community laboratory for completion of one of four screening algorithms based on past treatment experience (see figures 2, 3)

### Screening Procedures:

Participants with a positive HCV RNA will be accompanied to the lab for a serum lab draw and confirmatory lab draw ordered by the study clinician. Due to the health conditions that many participants are experiencing (dehydration, collapsed veins, etc.), it is likely that participants will need to return for a second confirmatory lab draw. Additional compensation will be provided if a second blood draw is needed. Research staff review screening survey and lab tests are entered into Child-Turcot-Pugh (CTP) calculator. Only participants with a CTP score of 6 or platelets < 150,000mm^3 will be referred for study clinician evaluation to confirm treatment eligibility; who will be blinded to treatment allocation until eligibility determined. All others will be fully screened by research assistant in the community. Once enrollment is confirmed, all participants will complete baseline surveys and randomization and then continue with treatment arm interventions as per Figure 1.

#### Central City Concern ONLY:

Participants with reactive antibody tests will also be offered participation in the hepatitis C and hepatitis B core antibody dried blood spot validation study, which would include performing a point of care dried blood spot test and completing confirmation serum HCV PCR and hepatitis B surface antibody testing. DBS specimens will be collected by peers and/or RAs and serum for confirmation by community partner laboratories. The DBS card will be shipped to Molecular Testing Laboratories for testing.

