### Intervention Design:

Central City Concern ONLY: Phase 1: Once in-house potential participants are identified they will be offered participation in the DBS study by IRB-trained CCC HCV team staff. Participants will provide a phlebotomy-derived blood sample and finger stick capillary blood sample for DBS card. These will be sent to MTL for DBS validation using standard human biohazard sample laboratory storage and shipping techniques consistent with MTL procedures. Incentives will be dispensed at the time of DBS sample collection or along with critical medications or services already provided, whichever method entails less on campus time for participants.

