#### Study Arm 2: Community Linkage-To Care Arm (Control Condition) Procedures:

Participants allocated to the community linkage-to-care arm will complete screening, be offered enrollment, and undergo informed consent as in the telemedicine arm. Following study inclusion and enrollment, research staff will refer the participant to a local community health clinic to engage in hepatitis C care and seek treatment. Peers will assist patients to engage with local primary care and health plan resources and will receive an information sheet on optional clinics to attend and questions to ask their provider. TAU participants will be encouraged to take this to their visit. Research assistants will outreach to participants regularly to determine if they have engaged in local health resources and schedule assessment visits. A bidirectional release of information will be requested. The study clinical pharmacist or research assistant will assess adherence medication adherence at week 4 and end of treatment via telephone. SVR12 laboratory testing will be performed by the community provider with at least one telephone reminder prior to lab due date. 12 weeks post end of treatment study assessments will coincide with SVR12 lab results visit and 36 week post end of treatment assessments performed as in the telemedicine arm.

Chart abstraction for participants in both arms will be performed in order to assess the number of and types of interactions the peers have with participants.

In either arm, participants who do not initiate treatment by 12 weeks after randomization will begin their assessment timeline, mirroring treatment timeline for an 8-week direct acting antiviral regimen. For these participants, the study research assistant will collect study assessments at week 16 (corresponding to 4-week post-treatment initiation), week 20-22 (corresponding to end of treatment visit), week 32 (corresponding to 12 weeks post-treatment visit), and week 56 (corresponding to 36

weeks post-treatment visit) after randomization; the primary study outcome will be assessed at 32 weeks after randomization.

Participant Assessments:

Phase 1:

- Blood draw and DBS specimen collection for HCV RNA and Hepatitis B core antibody

Phase 2:

Assessment/Activity	Pre-Screen	Screen	Baseline (Week 0)	4-Week after treatment initiation	End of Treatment	12-week Post-Treatment	***36-Week Post Treatment Completion	As Needed

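### Phase 1 contradicts itself on the serum reference for the hepatitis B dried blood spot test: one section names surface antibody, two others name core antibody

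*Combined protocol and SAP*

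**What the plan says.** The paragraph headed Central City Concern ONLY, under Screening Procedures, offers people with reactive antibody tests entry to a "hepatitis C and hepatitis B core antibody dried blood spot validation study". The same sentence says that taking part means a point-of-care DBS test and "completing confirmation serum HCV PCR and hepatitis B surface antibody testing".

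Two other Phase 1 sections name a different hepatitis B serum test:

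- Phase 1 Prescreening Procedures lists, among the items consented to, "Blood draw for hepatitis C RNA and hepatitis B core Antibody".
- The Phase 1 line under Participant Assessments reads "Blood draw and DBS specimen collection for HCV RNA and Hepatitis B core antibody", so the venous draw and the card carry the same two analytes.

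The Phase 1 text under Intervention Design describes the paired specimens only as a "phlebotomy-derived blood sample and finger stick capillary blood sample for DBS card" and names no analyte. On handling, Prescreening Procedures states: "The serum lab specimens collected for DBS validation will only be sent to Molecular Testing Laboratories for the purpose of DBS card validation". It adds that these results are not given to participants and are outside the study clinicians' laboratory review.

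**The concern.** A validation study compares an index test with a reference test for the same target. In the Central City Concern paragraph the index test is core antibody and the serum test called confirmation is surface antibody. Vaccination produces surface antibody but not core antibody. Disagreement between the two therefore mixes true serological difference with DBS error, and the data cannot separate them.

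Three features make the slip worth correcting before specimens are ordered:

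- This paragraph is the only Phase 1 text that labels a named serum test as the confirmation for the DBS study. Someone building an order set could reasonably work from it.
- The Data Analysis section contains no DBS accuracy analysis, so no analysis text settles which serum result is the hepatitis B reference.
- The validation results bypass clinician review and are not returned to participants, so no review described in the protocol would expose a wrong analyte.

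If the wrong serum test were run and the specimens not kept, the matched pairs might not be recoverable.

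**Working it through.** **Step 1: each section that names a hepatitis B analyte, side by side.**

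| Section | DBS analyte | Serum analyte |
|---|---|---|
| Screening Procedures, Central City Concern ONLY | core antibody | surface antibody |
| Phase 1 Prescreening Procedures (consent list) | not stated in the DBS item | core antibody |
| Participant Assessments, Phase 1 | core antibody | core antibody |
| Intervention Design, Phase 1 | not stated | not stated |
| Phase 2 assessment table | not applicable | surface antigen (listed twice), core antibody |

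Surface antibody appears once in the document. The sentence is complete, current procedural text, with no redaction or broken table.

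**Step 2: is there a figure to reproduce?** No. The plan gives no sensitivity, specificity, precision or power target for the hepatitis B DBS test. Phase 1 is sized on HCV alone: "An initial target sample of 100 Hepatitis C positive participants will be enrolled for DBS validation".

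**Step 3: what the wrong reference would do, on assumed values.** None of these inputs comes from the documents.

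- c = core antibody prevalence, 0.10 to 0.30
- s = share of core-positive people who are also surface antibody positive, 0.75
- v = share of core-negative people who are surface antibody positive through vaccination, 0.20 to 0.60

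Suppose the DBS core antibody test makes no errors. Against serum core antibody it scores 100% on both measures by construction. Against serum surface antibody:

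- apparent sensitivity = cs / [cs + (1 − c)v]
- apparent specificity = (1 − c)(1 − v) / [1 − cs − (1 − c)v]

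| c | v | Apparent sensitivity | Apparent specificity |
|---|---|---|---|
| 0.10 | 0.60 | 0.075/0.615 = 12% | 0.36/0.385 = 94% |
| 0.10 | 0.20 | 0.075/0.255 = 29% | 0.72/0.745 = 97% |
| 0.20 | 0.40 | 0.15/0.47 = 32% | 0.48/0.53 = 91% |
| 0.30 | 0.60 | 0.225/0.645 = 35% | 0.28/0.355 = 79% |
| 0.30 | 0.20 | 0.225/0.365 = 62% | 0.56/0.635 = 88% |

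The ranges are 12% to 62% and 79% to 97%.

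**Step 4: does this depend on fixing s at 0.75?** A second set of assumptions lets it vary. Let 10% to 20% of people have both antibodies, 10% to 40% surface antibody only, and 5% to 10% core antibody only. The share of core-positive people who also have surface antibody then runs from 0.10/0.20 = 50% to 0.20/0.25 = 80%.

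- Apparent sensitivity runs from 0.10/0.50 = 20% to 0.20/0.30 = 67%.
- Apparent specificity runs from 0.30/0.40 = 75% to 0.75/0.80 = 94%.

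The percentages move, but an error-free test looks inaccurate under both sets.

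**The case against.** The best defence is that this is a wording slip. A reader might infer that the investigators chose surface antibody as the reference, or that Phase 1 has no matching serum test for hepatitis B. The documents do not support either reading. Two sections specify a core antibody blood draw, and the Phase 1 assessment list pairs draw and card on that analyte. Staff following the whole protocol would obtain a matched core antibody result, with surface antibody as an extra.

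The Central City Concern paragraph also never says that accuracy will be calculated against surface antibody. Recruitment Methods uses the language of confirmation for usual clinical laboratory work, so the paragraph may have mixed clinical testing with validation testing. That is plausible but not established, because the sentence places the test inside the validation study.

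The figures above describe only the case in which that paragraph alone governs the order. They do not estimate the expected effect of the error.

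These points stand, and they limit the finding to a contradiction. They do not remove it: the three sections cannot all describe the same serum reference, and the plan does not say which one governs. The only planned check on Phase 1 size, "Power will be reassessed based on feedback from receiver operating curve model", does not name a hepatitis B reference either.

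**Conclusion.** The contradiction is real and should be corrected. It is an internal inconsistency and does not show a faulty choice of design. Harm is conditional: if sites or the laboratory order from the Central City Concern paragraph alone, the hepatitis B DBS test has no valid reference, and even an error-free test could show apparent sensitivity of about 12% to 62%. That range rests wholly on assumed serology. The direction rests on general knowledge that vaccination raises surface antibody and not core antibody. The contradiction itself needs neither.

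A reader might go further and conclude that the hepatitis B accuracy estimates will be meaningless, or that the trial is compromised. Neither follows. A matched core antibody draw is already specified in two sections. The HCV DBS validation has a consistent serum comparator, HCV RNA by PCR. Phase 2 is stated not to be contingent on Phase 1, so SVR12 and the secondary outcomes are unaffected.

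**What to change.** 1. In the Central City Concern paragraph, name serum hepatitis B core antibody as the paired reference for the core antibody DBS test, in line with Prescreening Procedures and Participant Assessments.
2. If surface antibody is also wanted, list it as an additional test with its purpose stated, separate from the reference.
3. Check that the laboratory requisition and order set carry the same analyte. If Phase 1 specimens have already been collected, confirm which hepatitis B serum test was run on them.
4. Add a sentence to Data Analysis giving the serum reference for each DBS analyte: HCV RNA and hepatitis B core antibody.

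The cost is about two lines of protocol wording and one check with the laboratory. The sample size and visit schedule do not change.
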